8.3. Missing Data

The primary method to impute the missing values will be as follows:

Continuous Endpoints: For continuous secondary endpoints (except EQ-5D, HADS) during treatment period, the MI under MAR assumption approach and the MMRM approach will be used to handle the missing data.

Binary Endpoints: All missing values will be treated as a non-responder for the binary endpoints for primary, key secondary and secondary endpoints. To assess the robustness of non-responder analysis for primary and key secondary endpoints, a tipping point analysis will be performed. The MI under MAR assumption, last observation carried forward (LOCF) approach, and observed case (OC) approach will be used as sensitivity analysis to impute the missing values for the primary and key secondary endpoints. If applicable, the continuous response will be imputed first, and the response will then be categorized.

Use of rescue therapy: All efficacy data, except OC, will be treated as treatment failure. Binary endpoints will be based on the underlying values and continuous variables will be imputed using the worst case score (questionnaires) or worst case value (diary data), on or after rescue therapy is used, independent if visit was attended or not. This procedure will be completed before imputing missing data under different assumptions (i.e., non-responder, LOCF, MI under MAR/MNAR). A different approach will be applied for MMRM analysis where data on or after rescue therapy will be considered as missing before applying MMRM analysis.

In OC analysis, no observed data after subject has received rescue treatment will be excluded. There will be no imputations for missing data.

Adverse events and concomitant medications/procedures: Missing assessment times will have imputed times for the purposes of assessing treatment emergence for AEs or classifying medications/procedures into prior/concomitant. However, the assessment date and time (start date, stop date, and time if collected from CRF) without imputation will be presented in the listings.

For the start of a concomitant medication/procedure or AE:

- Only the year is reported: If the subject received the first study drug dose in the year reported, then the date of the first dose of study drug will be used as the start date; otherwise, January 1 of the year reported will be used as the start date.

This document is confidential.

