Continuous secondary endpoints (except EQ-5D, HADS, and PN intensity) will be analyzed using multiple-imputation (MI) assuming MAR for missing data, including treatment group, analysis center and body weight at randomization cut-off (< 90 kg and \geq 90 kg) as factor and baseline as covariate where applies, and using mixed effect model for repeated measure (MMRM) approach, including visit, treatment group, analysis center and body weight at randomization cut-off (< 90 kg and \geq 90 kg) as factor, baseline, the interaction term between baseline and visit, and the interaction term between treatment group and visit as covariates. The estimated treatment difference for each endpoint at each visit will be displayed in the summary of statistical analysis together with the 95% CI and associated p-value. EQ-5D and HADS endpoints will be analyzed using ANCOVA including treatment group, analysis center and body weight at randomization cut-off (< 90 kg and \geq 90 kg) as factor and baseline as covariate. PN intensity will be analyzed using mixed effect model for repeated measure (MMRM) approach, including visit, treatment group, analysis center and body weight at randomization cut-off (< 90 kg and \geq 90 kg) as factor, baseline, the interaction term between baseline and visit, and the interaction term between treatment group and visit as covariates. All secondary endpoints will be presented descriptively using OC.

Note: The strategy of dealing with ICE will be the same as defined in [Table 7-2](#) for all secondary endpoints, unless it was specified (i.e., OC).

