AP NRS will be determined by an average as described above at every week from Baseline to Week 24 as a continuous variable. Descriptive summary of AP NRS will be provided on the ITT population. Absolute change and percent change from Baseline for the AP NRS score will also be included in the summary.

Absolute and percentage change from Baseline in PP/AP NRS will be analyzed using ANCOVA with MI assuming MAR for missing data including treatment group, analysis center and body weight at randomization cut-off (< 90 kg and \geq 90 kg) as factor and baseline as covariate, and using MMRM, including visit, treatment group, analysis center and body weight at randomization cut-off (< 90 kg and \geq 90 kg) as factor, baseline, the interaction term between baseline and visit, and the interaction term between treatment group and visit as covariates on ITT population. The least squares means (LSMeans), standard error of

This document is confidential.

LSMeans, and 95% CI for change from baseline, as well as the difference in LSMeans between the treatment groups, the two-sided 95% CI, and associated p-value will be presented.

Proportion of subjects with PP NRS at each analysis visit will be summarized:

- Improvement ≥ 4 from baseline
- < 2 at visit
- < 3 at visit

Proportion of subjects with AP NRS at each visit will be summarized:

- Improvement ≥ 4 in change from baseline
- < 2 at visit

The proportions of subjects will be presented on the ITT population using OC and non-responder for AP NRS and using OC, non-responder and LOCF for PP NRS. The estimate of treatment unadjusted and strata-adjusted proportion differences with the corresponding two-sided 95% CI, and p-values from the CMH test will be presented using non-responder.

Line plots for proportion of subjects with PP NRS improvement ≥ 4 and proportion of subjects with PP NRS < 2 using non-responder imputation will be presented on the ITT and PP population.

Additionally the weekly average PP NRS will be recalculated by using at least 2 assessments, or 3 assessments, instead of at least 4 assessments and without extending the visit window for sensitivity analysis.

The proportion of subjects with the weekly average PP NRS using 2, or 3 assessments, will be summarized at each analysis visit:

- PP NRS Improvement ≥ 4 from baseline
- PP NRS < 2

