10.3.4. Sleep Disturbance Numeric Rating Scale (SD NRS)

The SD NRS is a scale to be used by the subjects to report the degree of their sleep loss related to PN.

The Baseline SD NRS will be determined based on the average of daily SD NRS (score ranging from 0 to 10) during the 7 days up to the treatment start (including until treatment start time) (rounding to nearest whole number is not permitted). A minimum of 4 daily scores out of the 7 days up to Baseline study day is required for this calculation. SD NRS at all following visits will be determined following the rules described in [Table 8-2](#). If there are less than 4 non-missing assessments in the baseline diary window, the interval lower bound can be extended up to 7 additional days, one day at a time, to obtain the most recent 4 non-missing values.

This document is confidential.

Subjects will be asked the following question:

- “On a scale of 0 to 10, with 0 being ‘no sleep loss related to the symptoms of my skin disease (prurigo nodularis)’ and 10 being ‘I did not sleep at all due to the symptoms of prurigo nodularis’, how would you rate your sleep last night?”

Summary using OC will be provided on the ITT population. Absolute change and percentage change from Baseline will also be included in the summary.

Absolute and percentage change from Baseline at each analysis visits will be analyzed using ANCOVA with MI assuming MAR for missing data including treatment group, analysis center and body weight at randomization cut-off (< 90 kg and \geq 90 kg) as factor and baseline as covariate, and using MMRM, including visit, treatment group, analysis center and body weight at randomization cut-off (< 90 kg and \geq 90 kg) as factor, baseline, the interaction term between baseline and visit, and the interaction term between treatment group and visit as covariates on ITT population. The LSMeans, standard error of LSMeans, and 95% CI for change from baseline, as well as the difference in LSMeans between the treatment groups, the two-sided 95% CI, and associated p-value will be presented. Improvement in SD NRS will be calculated using Baseline as the reference point for change in SD NRS score.

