21.3. Example SAS Code

1. The example SAS code for CMH model is listed as below:

```
proc freq data=analysis_data;
  tables stratum*trt*resp/ cmh alpha=0.1;
run;
```

2. The example SAS code for MMRM model is listed as below:

```
proc mixed data = analysis_data;
  class stratum trtp avisit subjid;
  model chg = base stratum trtp avisit trtp*avisit/ ddfm=kr;
  repeated avisit / subject=subjid(trtp) type=un;
  lsmeans trtp/ cl diff;
  lsmeans trtp*avisit/ slice=avisit cl diff;
run;
```

3. The example SAS code for ANCOVA model is listed as below:

```
proc mixed data = analysis_data;
  class stratum trtp;
  model chg = base stratum trtp;
  lsmeans trtp/ cl diff;
run;
```

4. The example SAS code for imputation phase by PROC MI:

```
proc mi data=analysis_data seed=202685 minimum=xx maximum=xx nimpute=50 out=out_data;
  mcmc impute=monotone chain = multiple;
  var base stratum y4 y8 y12 y16;
run;

proc mi data = analysis_data seed=202685 minimum=xx maximum=xx nimpute=number_of_imputations
out=out_data;
  by imputation;
  class trtp stratum;
  monotone reg (/details); [OR montone logistic;]
  mnar model (y4 / modelobs = (trtp = 'Placebo'));
  mnar model (y8 / modelobs = (trtp = 'Placebo'));
  mnar model (y12 / modelobs = (trtp = 'Placebo'));
  mnar model (y16 / modelobs = (trtp = 'Placebo'));
  var base stratum y4 y8 y12 y16;
run;
```

This document is confidential.

5. The example SAS code for pooling phase for ANCOVA model by PROC MIANALYZE:

```
proc sort data=diff;
  by avisitn trtp;
run;

proc sort data=lsm;
  by avisitn trtp;
run;

proc mianalyze data=diff;
  by avisitn trtp;
  modeleffects estimate;
  stderr stderr;
ods output ParameterEstimates=estdiff; run;

proc mianalyze data=lsm;
  by avisitn trtp;
  modeleffects estimate;
  stderr stderr;
ods output ParameterEstimates=estlsm; run;
```

This document is confidential.

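### Two example-code lines in SAP 21.3 need correcting: the MMRM omits baseline-by-visit, and the MCMC gap-filling step ignores treatment arm (minor)

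*SAP*

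**What the plan says.** **MMRM.** SAP 10.3 lists visit, treatment, analysis center and weight group as factors, then "baseline, the interaction term between baseline and visit, and the interaction term between treatment group and visit as covariates". SAP 10.3.3 (pruritus NRS), 10.3.4 (sleep disturbance NRS) and 10.3.9 (DLQI) repeat this, and 10.3 applies the same model to PN pain intensity. The example in SAP 21.3, item 2, is "model chg = base stratum trtp avisit trtp*avisit/ ddfm=kr".

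**Role of these methods.** For continuous secondary endpoints, SAP 8.3 says "the MI under MAR assumption approach and the MMRM approach will be used to handle the missing data". They are therefore the planned methods there, not only sensitivity analyses.

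**Imputation.** SAP 21.2.1 describes two stages. First, MCMC makes the pattern monotone; no treatment term or by-arm run is mentioned. Second, a logistic or linear regression is fitted that does include treatment, the randomization strata and earlier assessments. SAP 21.3, item 4, prints the first stage as "mcmc impute=monotone chain = multiple", with the list "var base stratum y4 y8 y12 y16" and no BY or CLASS statement. It then prints one second-stage block, the placebo-based one, ending with the line that begins "mnar model (y16 / modelobs = (trtp = 'Placebo". That block uses the same variable list.

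**The concern.** A programmer who copies item 2 fits a different MMRM from the one in the text. The SAP does not say which prevails when text and example differ, and Section 18 plans nine MMRM tables.

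The MCMC step is a different kind of problem, because following the text does not cure it: 21.2.1 is silent on treatment at that stage. An imputation model that ignores arm draws a missing value from the mixture of both arms. An active-arm gap is then filled too much like placebo and a placebo gap too much like active, which usually pulls the difference toward zero. Section 18 plans nine ANCOVA tables using MI under MAR, and the primary and key secondary endpoints have MI sensitivity analyses.

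The step has two further weaknesses. With no CLASS statement, `stratum` (which the SAP does not define) enters as a number. And the list stops at Week 16, although these secondary endpoints are reported to Week 24 (Table 10-1; table 14.2.3.3.11).

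**Working it through.** The SAP states no figure to reproduce. The check compares text with code and then sizes the effect.

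**1. MMRM terms**

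| Term | SAP 10.3 | SAP 21.3 item 2 |
|---|---|---|
| baseline | yes | `base` |
| strata | center, weight group | `stratum` |
| treatment, visit | yes | `trtp`, `avisit` |
| treatment by visit | yes | `trtp*avisit` |
| baseline by visit | yes | absent |

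Simulated size (unstructured covariance, six visits, 12% MAR dropout, 250 trials per setting, baseline slope varying over visits by 0, 0.6 or 1.2): the mean shift in the treatment difference is at most 0.004 on about -2.0. The standard error is 0.31 to 0.33 either way. Within one trial the two models typically differ by 0.01 to 0.06.

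**2. What the MCMC step can reach.** With the list ending at `y16`, a gap is intermittent only if a later listed visit is observed. The step can therefore fill baseline and Weeks 4, 8 and 12, never Week 16.

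**3. Size at Week 4, closed form.** From SAP 4.3: 50% vs 20% responders (30 points) and 2:1 allocation. Assumed: those Week 16 rates hold at every visit, SD of change 2.4, between-visit correlation 0.65, gap rates of 2%, 5% and 10%.

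- Mean difference that gives 50% vs 20% at a fixed threshold: 0.8416 × 2.4 = 2.02.
- Within-arm variance 2.4² = 5.76; covariance 0.65 × 5.76 = 3.74.
- Between-arm variance (1/3)(2/3)(2.02²) = 0.91.
- Pooled variance 5.76 + 0.91 = 6.67; pooled covariance 3.74 + 0.91 = 4.65.
- Share of the arm difference kept when Week 4 is predicted from the three later visits: 3(4.65) / (6.67 + 2 × 4.65) = 87.4%; lost, 12.6%.
- Loss = gap rate × 12.6% × 30 = 0.08, 0.19 and 0.38 points.

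This treats the proportional loss in the mean as the loss in responder points, and it ignores baseline as a predictor.

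Other correlations, same formula:

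- 0.4: covariance 2.30 + 0.91 = 3.21; kept 9.63/13.09 = 73.6%; loss 0.16, 0.40 and 0.79 points.
- 0.8: covariance 4.61 + 0.91 = 5.51; kept 16.54/17.70 = 93.5%; loss 0.04, 0.10 and 0.20 points.

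**4. Simulation of the two-stage procedure.** Set-up: 180/90 subjects, 15% dropout, 50 imputations, pooled MCMC followed by the 21.2.1 regression with treatment, compared with MCMC by arm. At correlation 0.65 the Week 4 difference is lower by 0.05 to 0.10, 0.18 to 0.22 and 0.31 to 0.44 points at 2%, 5% and 10% gaps. Each range covers 20%, 50% or all dropouts leaving before Week 4. Mean PP NRS change at Week 4 is weaker by 0.004 to 0.030 on about -2.0. Week 16 shows no shift (-0.05 to +0.08, SE 0.03 to 0.05). With lists run to Week 24 and gaps at every visit from Week 4 to Week 20, the loss is 0.06 to 0.28 points.

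**5. Different assumptions.** If the effect instead grows from -1.5 at Week 4 to -2.5 at Week 16 (SD 2, correlation 0.4 to 0.8, gaps of 5% to 15%), pooled filling changes the Week 4 difference by between a 1.5% loss and a 0.3% gain. Attenuation is the usual direction, not a certain one.

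**The case against.** The section is headed as example code and is plainly a template: it has placeholders, and the second PROC MI call reads the original data set rather than the output of the first. The operative models are in the prose. SAP 21.2.1 also expects a monotone pattern, in which case the MCMC step fills nothing. SAP 8.3 sets values on or after rescue to the worst case before imputation, which removes some gaps; the simulation has no such rule. All gap rates are assumed.

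Most of this stands, and it keeps the point minor. It does not remove it: the MMRM line contradicts the text, and on the MCMC step the prose offers no correction.

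A reader might infer more, in four ways that the SAP does not support:

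- *That MAR imputation leaves treatment out altogether.* Doing so would attenuate the Week 16 difference by 1.1% to 5.9% at 5% to 15% missing (assumptions of working step 5). But 21.2.1 requires treatment in the regression step. Not printing an example of that step is an omission, not an error.
- *That the placebo-based block is wrong.* Having no treatment in its list is right for that method. Ending at Week 16 is also right, since 10.1.2, 10.2 and Section 18 plan control-based imputation only for Week 4 and Week 16 endpoints.
- *That the examples serve none of the planned tables.* The ANCOVA and pooling examples (items 3 and 5) do serve the MI-MAR tables.
- *That numeric coding of `stratum` does harm.* A two-level code would be harmless; the SAP does not say how many levels there are.

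**Conclusion.** The point holds, and is minor. The MMRM example omits a term that four sections require; the average consequence is negligible, but two programmers could report slightly different estimates. The MCMC step as printed pools the arms and 21.2.1 does not prevent it. Expect a loss of about 0.1 to 0.4 points on an assumed 30-point difference at visits with 2% to 10% intermittent gaps (up to about 0.8 at correlation 0.4), and none if missingness is monotone. Week 16 is not affected with the printed list. The primary and key secondary non-responder CMH analyses do not use either piece of code. The documentary part is certain. The sizes rest on assumed gap rates, SD and correlations, and on applying the Week 16 design rates to Week 4.

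**What to change.** 1. SAP 21.3 item 2: add `base*avisit` to the MODEL line.
2. SAP 21.2.1 and 21.3 item 4: include a 0/1 treatment indicator in the MCMC step, or run it by arm, and state the choice in 21.2.1. Define the strata and enter them as indicator variables.
3. For MI-MAR runs of secondary endpoints reported to Week 24, extend the MCMC and MAR regression lists to `y20` and `y24` (DLQI: `y4`, `y16`, `y24`). Leave the placebo-based list at `y16`, without treatment.
4. If the same MCMC step feeds the control-based run, amend 10.1.2 and 21.2.1 together. The text should say that intermittent gaps are filled within arm and that only the monotone step uses placebo data. As written, 10.1.2 allows only placebo observations, so changing 21.2.1 alone would create a new conflict.
5. Optional, for clarity: print the MAR regression step with treatment in CLASS and VAR, and state that the amended text governs over the examples.

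Cost: a few lines and no new data. Running MCMC by arm fits placebo on 90 subjects and is slightly noisier; in simulation the indicator version gives Week 4 results within 0.06 points of it.

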5.2. Key Secondary Efficacy Endpoints

The key secondary efficacy endpoints are as follows:

- Proportion of subjects with an improvement of ≥ 4 from baseline in PP NRS at Week 4
- Proportion of subjects with PP NRS < 2 at Week 16
- Proportion of subjects with an improvement of ≥ 4 from baseline in SD NRS at Week 16
- Proportion of subjects with an improvement of ≥ 4 from baseline in SD NRS at Week 4
- Proportion of subjects with PP NRS < 2 at Week 4

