10.3.3. Pruritus Numeric Rating Scale (NRS)

The Pruritus NRS is a scale to be used by the subjects to report the intensity of their pruritus (itch) during the last 24 hours. Peak pruritus (PP NRS) is an assessment of the maximum itch intensity in that period while average pruritus (AP NRS) provides a measure of overall pruritus intensity.

Subjects will be asked the following question:

- For maximum itch intensity (PP NRS): "On a scale of 0 to 10, with 0 being 'no itch' and 10 being the 'worst itch imaginable', how would you rate your itch at the worst moment during the previous 24 hours?"
- For average itch intensity (AP NRS): "On a scale of 0 to 10, with 0 being 'no itch' and 10 being the 'worst itch imaginable', how would you rate your itch overall during the previous 24 hours?"

The screening PP/AP NRS will be determined by a single assessment using the PP/AP NRS (score ranging from 0 to 10) for the 24-hour period immediately preceding the screening visit.

The Baseline PP/AP NRS will be determined based on the average of daily PP/AP NRS (score ranging from 0 to 10) respectively during the 7 days immediately preceding Baseline (rounding to nearest whole number is not permitted). A minimum of 4 daily scores out of the 7 days immediately preceding Baseline (up to one day before date of first treatment) is required for this calculation. If there are less than 4 non-missing assessments in the baseline diary window, the interval lower bound can be extended up to 7 additional days, one day at a time, to obtain the most recent 4 non-missing values.

PP/AP NRS at all follow-up visits will be determined in the same manner, however if the intake date of rescue therapy is before and on the last day of the weekly visit window, this week will be treated as treatment failure except for OC analysis and the weekly average will be imputed using the worst case value, see [Section 8.3](#).

Subjects will receive instructions on how to record their PP/AP NRS scores and will complete the assessment once daily in the evening throughout the clinical study (including the run-in and the follow-up period).

PP NRS will be determined by an average as described above at every week from Baseline to Week 24 as a continuous variable.

Descriptive summary of PP NRS will be provided on the ITT and PP populations using observed cases. Absolute change and percentage change from Baseline for the PP NRS will also be included in the summary on the ITT and PP populations.

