21.2.1. Imputation Phase

50 imputed datasets with a monotone missing pattern will be created using SAS MI procedure based on the observed data (Markov-Chain-Monte-Carlo method, MCMC). The seed to be used is 202685 (the Protocol number). Pattern of missing data will be evaluated and it is expected that the pattern of missing data will be monotonic. For non-monotone missing data patterns, MCMC method of MI procedure will be used to impute enough data so that the remaining missing data is monotone.

Each of the imputed datasets will be used to generate 50 complete datasets, using following approaches:

- Binary endpoint: A logistic regression method to impute the ordinal missing data, including treatment, randomization strata, and assessments from earlier time points as covariates. Response or total score of the subjects will be derived using these imputed data.
- Continuous endpoint: A linear regression model including treatment, randomization strata, and assessments from earlier time points as covariates will be used to impute the score. Response or total score of the subjects will be derived using these imputed data.

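### The only imputation model printed for the diary scores uses Weeks 4, 8, 12 and 16; SAP 21.2.1 should name the weekly averages that precede each target visit

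*SAP*

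**What the plan says.** **Imputation text (SAP 21.2.1).** For continuous scores: "A linear regression model including treatment, randomization strata, and assessments from earlier time points as covariates will be used to impute the score". The binary paragraph names the same covariates. Neither says whether the earlier time points are weekly or monthly.

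**Code (SAP 21.3, item 4).** Under the label "4. The example SAS code for imputation phase by PROC MI", both PROC MI steps carry the same list: "var base stratum y4 y8 y12 y16". No other part of the SAP names time points for the imputation.

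**Data available (SAP 8.4, Table 8-2, and 10.3.3).** Diary averages are derived for each week from 1 to 24. For PP NRS: "PP NRS will be determined by an average as described above at every week from Baseline to Week 24 as a continuous variable". Section 10.3.3 says the same of AP NRS, and Table 8-2 covers SD NRS.

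**Where MI is used.** In 8.3 and 10.1.2, MI under MAR is a sensitivity analysis for the primary and key secondary binary endpoints, whose main rule is non-responder imputation. On order, 8.3 says: "If applicable, the continuous response will be imputed first, and the response will then be categorized". In 8.3 and 10.3, MI is a main method beside MMRM for most continuous secondary endpoints, including PP, AP and SD NRS change.

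**The concern.** One co-primary and all five key secondary endpoints come from the daily diary. Three key secondaries are at Week 4, for example "Proportion of subjects with PP NRS < 2 at Week 4". For these, the printed list has no post-baseline score before the target. For later visits, up to three of the most recent weekly averages go unused.

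MAR given baseline, treatment and stratum is a much stronger assumption than MAR given the last weeks of diary as well. If subjects stop recording because they are not improving, a model without those weeks imputes them close to the average of their arm. At stake are the arm-level response rates in the MI sensitivity analyses, the MI-ANCOVA estimates of change, and the precision of both.

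**Working it through.** The SAP states no figure on this point, so there is nothing to reproduce. The check has four parts.

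**1. Listed against derived weeks.** Listed: 4, 8, 12, 16. Derived: 1 to 24. Up to Week 16 the unused weeks are 1-3, 5-7, 9-11 and 13-15.

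**2. How many subjects lack a Week 4 score.** From SAP 4.3: 270 subjects, 15% dropout over the treatment period. Assumption: dropout is even over 24 weeks.
- Total: 270 × 0.15 = 40.5.
- Before Week 4: 40.5 × 4/24 = 6.75, or 2.5% of 270.
- Before Week 16: 40.5 × 16/24 = 27.

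Dropout is not the only source. A weekly average needs at least 4 daily scores (8.2, 10.3.3), entries outside the clock limits in 8.4 are not used, and Table 8-2 extends the window only for baseline and Week 16. The SAP does not allow the Week 4 total to be fixed, so 2.5-10% is used as a range.

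**3. How much the weekly scores predict.** Assumed correlations, not in the SAP: baseline with any later week r_b = 0.2-0.4; two post-baseline weeks d apart, rp + (1 − rp) × a^d, with rp = 0.3-0.5 and a = 0.8-0.9. R² = c′S⁻¹c, where S is the correlation matrix of the predictors and c their correlations with the target.

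| Target; last recorded week is 3 | Baseline only (r_b²) | Baseline + Weeks 1-3 |
|---|---|---|
| Week 4 | 0.04-0.16 | 0.74-0.90 |
| Week 16 | 0.04-0.16 | 0.14-0.42 |

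For Week 4, the ratio of unexplained variance runs from 0.84/0.26 = 3.2 to 0.96/0.10 = 9.6.

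**4. Size of the bias at Week 4, by simulation.** Inputs, all assumed except the arm sizes: 180/90 subjects; weekly correlation 0.80 or 0.92; 2.5%, 5% or 10% missing; missingness rising with lack of improvement in Week 3 (logistic slope 0.3 or 0.6 per point); 400 trials per scenario; treatment in the imputation model, as 21.2.1 requires.
- True response among missing nemolizumab subjects: 12-27%.
- Imputed without Weeks 1-3: 43-46%. With Weeks 1-3: 11-27%.
- Active-arm rate overstated by 0.3-2.4 points; with weekly covariates, by 0.1 or less.
- Mean-change difference attenuated by 0.01-0.12 of about 2.16 points.

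A separate run over the same missing range gives 0.4-2.3 points for the active arm, 0.1-0.5 points for the response difference (placebo is overstated too), and attenuation of 0.01-0.13 of about 2.2 points (0.01/2.2 = 0.5% to 0.13/2.2 = 6%). Between-imputation variance is about 3-6 times larger without the weekly scores.

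Hand check: bias in an arm ≈ share missing × (imputed − true rate). With equal missingness in both arms, this is bracketed by 0.025 × (43 − 27) = 0.4 and 0.10 × (46 − 12) = 3.4 points. The simulated values lie towards the lower part because this mechanism puts more of the missing data in placebo.

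**The case against.** The strongest reply is that the code is an illustration. It is labelled an example, and 21.2.1 would permit weekly values. The list cannot be the model for every endpoint: it stops at Week 16 although Table 10-1 plans ANCOVA at Weeks 20 and 24; it includes Weeks 8 and 12 although the DLQI is not collected then; and it omits treatment, which 21.2.1 requires. The simulation itself takes treatment from the text, and if the text governs there, it governs the time points too. All of this stands. A reader might infer that the plan fixes the model at four visits or contradicts itself on timing. It does not; it leaves the choice open and illustrates only the monthly version.

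Other limits also stand:
- **Baseline alone** would be too strong. Stratum enters through the code and treatment through the text. For a gap followed by a later listed visit, the MCMC step can use that visit.
- **Week 16.** A reader might infer that Weeks 13-15 are all lost. Footnote b of Table 8-2 extends a Week 16 window with fewer than 4 scores by 5 days up, then up to 5 days down. For PP NRS that reaches Days 101-105, inside Week 15 (Days 99-105). A subject who completed Week 15 and then stopped therefore usually has a Week 16 value, and the loss is mainly Weeks 13-14. No bias figure is claimed for Week 16.
- **Non-improvers.** Rescue users are set to the worst value before MI (8.3), and those who stop study drug are asked to continue the diary (4.1). The mechanism applies to subjects whose diary stops without rescue use.
- **Other analyses.** Tipping-point, control-based, LOCF and observed-case analyses stand beside MI under MAR, and attenuation of a mean difference is conservative.

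**Conclusion.** The point holds as a cheap improvement to an under-specified model. A programmer following 21.2.1 and 21.3 together would most naturally use four visits, and a missing Week 4 diary score would then be imputed with no earlier post-baseline score.

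A reader might infer that the co-primary or key secondary conclusions are at risk. They are not: they rest on non-responder imputation. The effect falls on the MI sensitivity analyses of the PP NRS co-primary and the key secondaries, and on the MI-ANCOVA of PP, AP and SD NRS change. At Week 4 it is modest: up to about 2.3 points on the active-arm rate, at most 0.5 points on the difference, and up to about 6% attenuation of the mean-change difference, with clearly inflated imputation variance. At the roughly 2.5% missing implied by even dropout, the size is at the low end. The figures depend on the assumed correlations, the 2.5-10% missing, and missingness driven by Week 3 improvement; none of these is in the SAP.

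**What to change.** In 21.2.1, state that for PP, AP and SD NRS the imputation model contains treatment, randomization strata, baseline and the weekly averages before the target visit: at least Weeks 1-3 for Week 4, and the weeks immediately before each later visit. State in advance a reduced list to use if the model does not converge. Align the VAR list in 21.3, including treatment for the MAR run. Leave IGA and the questionnaires on their scheduled visits.

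The cost is SAP wording and a longer variable list, with no new data. The downside is more collinear and partly non-monotone variables, so a convergence check is needed. The change should be fixed before unblinding.
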